#### A3a. Financial Conflict of Interest

Does any member of study personnel (Investigator (including investigator's spouse and/or dependent children)) that are involved in the design, conduct, or reporting of the research have a Significant Financial Interest (SFI) that would reasonably appear to be affected by the research for which funding is sought and/or associated with an entity/business that would reasonably appear to be affected by the research?

No

**A5. Funding Source:**

Organization: TEXAS HIGHER EDU COORD. BRD

**A6a. Institution(s) where work will be performed:**

BCM: Baylor College of Medicine

TCH: Texas Children's Hospital

**A6b. Research conducted outside of the United States:**

Country:

Facility/Institution:

Contact/Investigator:

Phone Number:

If documentation of assurances has not been sent to the Office of Research, please explain:

**A7. Research Category:****A8. Therapeutic Intent**

Does this trial have therapeutic intent?

Yes

**A9. ClinicalTrials.gov Registration**

Does this protocol/trial require registration on ClinicalTrials.gov due to it: meeting the definition of an Applicable Clinical Trial, being required under the terms and conditions of an award, or being proposed to be published in ICMJE journals?

Yes

Who will be responsible for registering and maintaining the registration of this Applicable Clinical Trial?

The BCM PI will register the trial because either:

- the trial is BCM PI-initiated,
- BCM is the lead site of this multicenter trial, or,
- the industry sponsor has instructed the BCM PI to register the trial, or,
- registration of this trial is required as a term and condition of the reward by the funding agency.

ClinicalTrials.gov Identifier:

NCT03720795

**Section B: Exempt Request****B. Exempt From IRB Review**

Not Applicable

**Section C: Background Information**

Autism spectrum disorder (ASD) affects as many as 1 out of 59 individuals, with many higher-functioning youth not diagnosed until school-age or later. This equates to ~102,000 children under the age of 14 years in the state of Texas alone. Significant impairment in social and adaptive functioning are common, as are comorbid behavioral health disorders, with anxiety disorders affecting between 50-80% of youth with ASD. Given the relative frequency of anxiety disorders among children with ASD, the associated impairment, and worsening trajectory over time without intervention, there is a great need for treatment that specifically addresses anxiety-related symptoms in ASD.

Cognitive behavioral therapy (CBT) has demonstrated efficacy in a number of studies. However, existing treatment

protocols are delivered by therapists as ‘full-packages’ (i.e., 12-16 clinic sessions), which can be therapist-intensive, costly, impractical for families, and not responsive to parental preferences. Alternative approaches, such as parent-led, stepped-care models that improve accessibility, are efficient, provide personalized care, and lower mental health treatment cost, are greatly needed. Stepped-care models provide a lower-intensity first step (e.g., parent-led, less costly, and more convenient for parents) as the initial treatment with the assumption that a proportion of individuals will respond to the first step and others will need to step up to more intensive treatment. Matching treatment to families’ needs and tailoring subsequent treatment may be an efficient and effective approach, as well as consistent with parents’ desire to help their child. Given this, together with the substantial impairment associated with clinical anxiety in individuals with ASD across the age span, this study proposes to implement a parent-led, flexible, individually-tailored cognitive-behavioral intervention for children with ASD and anxiety.

## Section D: Purpose and Objectives

The purpose of this study is to implement a parent-led, stepped-care cognitive behavioral therapy to children with ASD and anxiety. Specifically, we will (1) examine the effectiveness of Stepped-Care CBT (SC-CBT; e.g., starting with Step One parent-led, therapist-assisted treatment and then either maintenance or Step Two therapist-directed CBT), (2) examine the potential predictors of response to Step One that could be used as baseline tailoring variables to match children to the best level of care (i.e., Step One or CBT), and (3) examine the economic value of using a cost-effectiveness approach of SC-CBT. We expect that through Stepped-Care CBT, children’s anxiety levels will lessen.

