**Section F: Design/Procedure****F1. Design**

Select one category that most adequately describes your research:

d) Questionnaire/survey/interview

Discuss the research design including but not limited to such issues as: probability of group assignment, potential for subject to be randomized to placebo group, use of control subjects, etc.

A total of 200 children (aged 4-14) with a diagnosis of ASD and co-occurring anxiety and their parent/legal guardian will participate and receive SC-CBT treatment. In addition, all participants will be asked to cooperate in assessments that will occur at baseline, mid-treatment, post-treatment, and 3-month follow-up.

Inclusion Criteria:

- 1) The child is between the ages of 4 to 14 upon enrollment with a) an established diagnosis of ASD made by a standardized assessment (e.g., Autism Diagnostic Observation Schedule-Second Edition; Childhood Autism Rating Scale-Second Edition); and/or b) a score of 65 and above on the Social Responsiveness Scale-Second Edition (SRS-2).
- 2) The child has clinically elevated symptoms of anxiety and/or OCD as indicated by a Clinical Severity Rating of  $\geq 4$  from the Anxiety Disorders Interview Schedule (ADIS), made on diagnoses endorsed on the Mini-International Neuropsychiatric Interview for Children and Adolescents (MINI-Kid) at baseline assessment, and the Pediatric Anxiety Rating Scale  $> 12$ .
- 3) Anxiety and/or OCD is the primary presenting problem and the independent evaluator (IE) determines that the child is appropriate for the intervention focus.
- 4) One parent/guardian is able and willing to participate (i.e., parent-led therapist assisted treatment, attend study assessments).
- 5) The child has a Full Scale and Verbal Comprehension IQ  $> 70$  as assessed on the Differential Ability Scales-Second Edition (DAS-II) or Wechsler Abbreviated Scale of Intelligence-Second Edition (WASI-II). This level of intellectual ability is frequently used to demarcate the boundary of "high functioning"  $\pm$  ASD, and we and others have adopted this in our CBT trials for children with ASD to achieve acceptable external validity.
- 6) Both parent and child are able to read and/or understand English

Exclusion Criteria:

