**STEP ONE.** All participants will start with Step One, which includes 4 parent-led, therapist-assisted sessions over a 12-week period. Parents will receive a parent-child workbook to use in session with the therapist, and at home. During each of these 4 sessions, the therapist will review with parents the necessary skills for conducting exposures and will provide guidance in the delivery of exposures. Exposures, a hallmark of CBT for anxiety are used to gradually and repeatedly confront feared stimuli. For example, exposure therapy for a child fearful of dogs may begin with looking at pictures of dogs and standing across the park from a dog on a leash, to eventually petting a dog. Outside of session, parents will lead therapy using the provided workbook, which consists of a step-by-step approach for parents written on a 6th-grade level. Brief phone contacts between parent and staff will also be provided for support, coaching, and motivation. After completing Step One, a brief assessment will occur (i.e., the mid-treatment). If the child meets treatment response status, then the parent and child end treatment and proceed to the Maintenance phase, where parents and children will be encouraged to continue using the workbook and tools that they learned in Step One. If the child does not meet treatment response (i.e., does not improve), then s/he will 'step up' to Step Two.

**STEP TWO.** For those children who do not respond to Step One, they will be 'stepped up' to Step Two, which consists of 10 therapist-led, parent-supported sessions, each lasting 60-120 minutes over the course of 12 weeks. During Step Two, therapists will lead exposure tasks and teach children response strategies. These strategies will focus on providing children with anxiety-coping skills. In addition, parents will be taught (in weekly sessions) to support children in learning and maintaining anxiety-coping skills, especially when outside of sessions. These skills are encouraged to be practiced at school, in the community, and in peer-group settings. After completing Step Two, participants will end treatment and the post-assessment will occur. For those participants in the maintenance phase (i.e., treatment responders at Step One), the post-assessment will occur approximately 12 weeks after the completion of the mid-treatment (for consistency with procedures in Step Two). All participants will then be re-assessed 3-months, after completion of the post-treatment.

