#### G2. Data Analysis

Provide a description of your plan for data analysis. State the types of comparisons you plan (e.g. comparison of means, comparison of proportions, regressions, analysis of variance). Which is the PRIMARY comparison/analysis? How will the analyses proposed relate to the primary purposes of your study?

Data analysis will involve Multilevel Modeling (MLM) because of the *nesting* nature of the variables. More specifically, because the measures are repeated, the measures are considered the first level of the hierarchy, the individual children are considered the second level, and the treatment groups are considered the third level. A major advantage of MLM is its ability to handle missing data. While more traditional analyses use listwise deletion if a single time point is missing, MLM uses parameter estimates to maximize the use of existing data. Furthermore, the present study will implement a regression discontinuity analysis, which is an application of mixed models within MLM. This will allow us to examine the impact of treatment, without the use of random assignment, as this method allows for the use of groups that are similar at baseline, but then are designated by a predetermined selection cut point.

After assessing responder status and determining which participants receive Step Two treatment and which participants move to the maintenance phase, binary logistic regression will be utilized in an attempt to determine if there are factors significantly predicting group membership. Possible predictors include variables such as age, anxiety severity, internalizing/externalizing problems, and parent characteristics.

Cost-effectiveness analysis examines the relative value of SC-CBT (relative to CBT). CEA is performed from a societal perspective, meaning the costs to the healthcare system and the patient/parents are included. Treatment costs include

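### Aim 2 can identify baseline predictors of Step One response, but this design cannot show that they match children to Step One or CBT as a starting level

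*Combined protocol and SAP*

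**What the plan says.** Section D sets the second aim as a task and a use. The task is to "examine the potential predictors of response to Step One that could be used as baseline tailoring variables". The use is that these predictors "could be used as baseline tailoring variables to match children to the best level of care (i.e., Step One or CBT".

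The treatment part of F2 fixes the sequence: "All participants will start with Step One, which includes 4 parent-led, therapist-assisted sessions over a 12-week period". Therapist-led treatment comes later and only for some: "For those children who do not respond to Step One, they will be 'stepped up' to Step Two". Children who respond go to maintenance. F1 describes a single group of 200 children, all of whom receive stepped care.

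For this aim, G2 plans that "binary logistic regression will be utilized in an attempt to determine if there are factors significantly predicting group membership". The groups are Step Two and maintenance, so the outcome is non-response versus response to Step One. The candidate predictors are examples such as age, anxiety severity, internalizing and externalizing problems, and parent characteristics. No term for starting treatment, and no interaction with it, is mentioned.

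**The concern.** Choosing a starting level for a child requires knowing how the difference in outcome between the two levels varies with the baseline factor. A model fitted to children who all began at one level gives the chance of success at that level only. It is a prognostic model.

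The two are easily confused. A factor that predicts poor response to Step One may predict equally poor response to therapist-led CBT, and matching on it would then send children to the more intensive step for no gain. It may instead mark the children who gain most, and matching would then be sound. If the published conclusion follows the wording of the aim, readers may take a prognostic result as evidence for treatment selection.

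**Working it through.** **The plan's own figure.** The only number attached to the aims is the total of 200, which G1 calls sufficient for the primary and secondary aims. It cannot be reproduced for this aim, because G1 gives no alpha, power, effect size or response rate, only a rule of 20 per group per level. With two groups and three levels the rule gives 20 x 2 x 3 = 120, or 120/(0.93 x 0.85) = 152 after both attrition rates. The argument below does not depend on the sample size.

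**Inputs from the documents.** Children starting with Step One: 200 of 200. Children starting with therapist-led CBT: 0. Attrition at Step One is about 7% (G1), so about 200 x 0.93 = 186 children would supply a Step One outcome.

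**Estimability.** Let x be a baseline factor and A the starting treatment (0 = Step One, 1 = CBT). A model that could inform matching has columns [1, x, A, A·x]. With A = 0 for every child, the last two columns are zero and the matrix has rank 2 of 4. The intercept and the effect of x on Step One response can be estimated. The effect of starting treatment and the interaction cannot. With children at both starting levels, the rank is 4.

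**What this leaves open.** Assume Step One response of 60% with a favourable factor and 30% without it. The documents give no rates, so these are illustrative. Gain = CBT-first rate minus Step One rate. Interaction = gain without the factor minus gain with it.

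| CBT-first response, with / without factor | Gain with | Gain without | Interaction |
|---|---|---|---|
| 80% / 50% | 80 - 60 = 20 | 50 - 30 = 20 | 0 |
| 60% / 60% | 60 - 60 = 0 | 60 - 30 = 30 | +30 |
| 90% / 30% | 90 - 60 = 30 | 30 - 30 = 0 | -30 |

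The Step One data are identical in all three rows. In the first row the factor does not change the gain. In the second, the low-response group gains more. In the third, it gains nothing.

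**How far Step One data bound the answer.** Suppose further that CBT first is never worse than Step One. The gain is then at most 100 - 60 = 40 points with the factor and 100 - 30 = 70 without it. The interaction can lie anywhere from 0 - 40 = -40 to 70 - 0 = +70, so its sign is not determined.

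**Whether other planned data fill the gap.**
- Step Two outcomes: the CBT-first response rate at a given x is an average over children who would and would not have responded to Step One. The first kind never receive Step Two. The second kind receive it only after 12 weeks of Step One.
- Regression discontinuity (G2): it uses groups formed at a cut point, and the only such split described follows Step One. It contrasts Step Two with maintenance near that cut point, not two starting levels.
- Cost-effectiveness (G2): CBT is named as a comparator, but no source of CBT outcomes is described.

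**The case against.** The strongest reply is that the operative task is to examine predictors of Step One response, which the logistic model fits, and that the tailoring clause is a hedged later use. This stands. A reader might infer that the trial cannot answer Aim 2 at all, or that the aim guarantees usable tailoring variables. The documents do not support either reading: the predictors are called potential, and the use is something that could follow. Nor does G2 contain a rule or threshold that would assign a low-response group to CBT. It only looks for factors associated with group membership.

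A second reply is that predicted Step One response bears on who can remain at the lower-intensity step, which is the stepped-care rationale in Section C, and that it limits the benefit forgone. If predicted response were 90%, CBT first could add at most 100 - 90 = 10 points. This also stands, but a ceiling on gain does not say which children gain, as the -40 to +70 range shows.

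Third, no participant is allocated by these predictors, since step-up follows observed response at mid-treatment. That is correct. The consequence lies in what may be concluded, not in the conduct of the trial.

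The hedges do not rescue the named use. They express doubt about which predictors will emerge, whereas the missing element is any CBT-first outcome.

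**Conclusion.** The concern holds for the matching clause only. The planned regression can address baseline prognostic factors for Step One response. It cannot support choosing between Step One and CBT as a starting level, because 0 of 200 children start with CBT and the required interaction is not estimable at any sample size. With the assumed rates, the same data are compatible with interactions of 0, +30 and -30 points, so matching on predicted Step One response is neither shown to be right nor shown to be wrong.

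This reads CBT in Aim 2 as therapist-led treatment, following the contrast that Section D draws, and takes the aim as a choice made at baseline. It also assumes that no CBT-first data are described in the Section S attachments, which are not among the documents available. The fidelity section refers to both conditions, but no CBT-first condition is defined. The response rates are illustrative; the lack of estimability does not depend on them.

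**What to change.** In Section D, state Aim 2 as examining baseline prognostic factors for response to Step One. Delete the clause on matching children to a level of care, or mark it as a hypothesis for a later study.

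In G2, add that conclusions from the logistic regression are limited to the predicted chance of Step One response, and that choosing a starting level needs data from children who start at either level.

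This changes wording only. The model, the sample size, the assessments and the data collected stay as they are. The downside is a narrower claim.

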## Section E: Protocol Risks/Subjects

### E1. Risk Category

Category 2: Research involving greater than minimal risk, but presenting the prospect of direct benefit to the individual subjects.

### E2. Subjects

Gender:

Both

Age:

Adolescent (13-17 yrs), Adult (18-64 yrs), Child (3-12 yrs)

Ethnicity:

All Ethnicities

Primary Language:

English

Groups to be recruited will include:

Both patients and healthy, non-patient, normals

Which if any of the following vulnerable populations will be recruited as subjects?

Children, Mentally ill

Vulnerable populations require special protections. How will you obtain informed consent, protect subject confidentiality, and prevent undue coercion?

We will seek consent from all participants who wish to participate in this study. If and when a potential participant chooses to participate in this study, written informed consent will be obtained. Participants will be provided with all relevant information and will be given as much time as needed to decide whether to participate. Participants will be informed that their participation or absence of participation will not have any influence on the clinical services received at BCM, TCH, or any other institution. Informed consent will be obtained prior to proceeding with any study procedures.

We will take all appropriate steps to protect participants' identities. Participants will be assigned a unique alphanumeric identifier that will enable the research team to manage the participant data while maintaining the participant's confidentiality. All study data will also be coded with the participants’ unique identifier. The coded data will be stored on servers managed by the institutional IT programs and/or departmental system administrators. Any physical data will be examined in a secure and private environment. When not in use, the physical data will be locked in a filing cabinet located in the research team's office, where only the research team has access. We will collect the minimum amount of information needed for the purposes of this study. Only approved study personnel will have access to this data, and all of the information gathered will be used for this study, only unless data has clinical relevance to the patient’s treatment, in which case will be shared with the clinical team.

### E3. Pregnant woman/fetus

Will pregnant women and/or fetuses (as described in 45 CFR 46 Subpart B) be enrolled in the research?

No

**E4. Neonates**

Will neonates of uncertain viability or nonviable neonates (as described in 45 CFR 46 Subpart B) be enrolled in the research?  
No

**E5. Children**

Will children be enrolled in the research?

Yes

**Section F: Design/Procedure****F1. Design**

Select one category that most adequately describes your research:

d) Questionnaire/survey/interview

Discuss the research design including but not limited to such issues as: probability of group assignment, potential for subject to be randomized to placebo group, use of control subjects, etc.

A total of 200 children (aged 4-14) with a diagnosis of ASD and co-occurring anxiety and their parent/legal guardian will participate and receive SC-CBT treatment. In addition, all participants will be asked to cooperate in assessments that will occur at baseline, mid-treatment, post-treatment, and 3-month follow-up.

Inclusion Criteria:

- 1) The child is between the ages of 4 to 14 upon enrollment with a) an established diagnosis of ASD made by a standardized assessment (e.g., Autism Diagnostic Observation Schedule-Second Edition; Childhood Autism Rating Scale-Second Edition); and/or b) a score of 65 and above on the Social Responsiveness Scale-Second Edition (SRS-2).
- 2) The child has clinically elevated symptoms of anxiety and/or OCD as indicated by a Clinical Severity Rating of  $\geq 4$  from the Anxiety Disorders Interview Schedule (ADIS), made on diagnoses endorsed on the Mini-International Neuropsychiatric Interview for Children and Adolescents (MINI-Kid) at baseline assessment, and the Pediatric Anxiety Rating Scale  $> 12$ .
- 3) Anxiety and/or OCD is the primary presenting problem and the independent evaluator (IE) determines that the child is appropriate for the intervention focus.
- 4) One parent/guardian is able and willing to participate (i.e., parent-led therapist assisted treatment, attend study assessments).
- 5) The child has a Full Scale and Verbal Comprehension IQ  $> 70$  as assessed on the Differential Ability Scales-Second Edition (DAS-II) or Wechsler Abbreviated Scale of Intelligence-Second Edition (WASI-II). This level of intellectual ability is frequently used to demarcate the boundary of "high functioning"  $\pm$  ASD, and we and others have adopted this in our CBT trials for children with ASD to achieve acceptable external validity.
- 6) Both parent and child are able to read and/or understand English

Exclusion Criteria:

Participants will be excluded if (1) the child has a diagnosis of child lifetime DSM-5 bipolar disorder, psychotic disorder, and/or intellectual disability; (2) the child has severe current suicidal/homicidal ideation and/or self-injury requiring medical intervention (referrals will be made for appropriate clinical intervention); (3) the child is receiving concurrent psychotherapy for anxiety; (4) child has initiated or changed dosage of psychotropic medications within 4 weeks before study enrollment OR stimulant or benzodiazepine medications within 2 weeks before study enrollment. If appropriate, the child may be enrolled in the study once medication dosage has stabilized (i.e., 4 weeks for psychotropic medication or 2 weeks for stimulant/benzodiazepine medication).

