#### INITIAL PHONE SCREEN.

Parents will be given a 20-minute telephone screening to elicit preliminary inclusion/exclusion information. Individuals who meet basic eligibility requirements during the phone interview and remain interested will be invited for a screening visit (i.e., baseline assessment), at which point a member of the research team will obtain informed consent from the parent and child.

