#### INFORMED CONSENT

If and when a potential participant chooses to participate in this study, informed consent will be obtained. Participants will be provided with all relevant information and will be given as much time as needed to decide whether to participate. Participants will be informed that their participation or absence of participation will not have any influence on the clinical services received at TCH (or any other institution). Informed consent will be obtained prior to proceeding with any study procedures. All participants will also be informed that they do not have to answer any specific questions if they do not wish to do so. After obtaining consent, participants will complete the baseline assessment and begin treatment.

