#### TREATMENT

All participants will receive parent-led, stepped-care cognitive-behavioral therapy (SC-CBT). CBT focuses on how a child's thoughts, beliefs, and attitudes affect feelings and behavior and teach children coping skills for dealing with different problems. The type of CBT that will be used is a specialized program for children and adolescents with ASD and comorbid anxiety. This type of treatment will be delivered using a stepped-care model, which provides therapy in "steps" that vary by intensity. Treatment is "stepped-up" until the child begins to show improvement in anxiety symptoms, beginning first with the lowest intensity (e.g., fewer in-person appointments, parent-led exposures) to more intensive (e.g., weekly in-person sessions, therapist-led exposures), as needed. SC-CBT consists of two main steps (detailed below). Each participant will be treated by a licensed psychologist/therapist or trainee under the supervision of a licensed psychologist. At the end of study participation, a standardized summary of assessment and treatment will be provided to research participants. Assessment summaries will contain information about inclusion criteria (e.g. SRS score, CSR score, PARS score, whether they met IQ cut off, etc.). It will be specified that this summary details research findings, and that our assessment is not equivalent or a substitution of a clinical evaluation. Treatment summaries will contain information about how many therapy sessions participants attended. Summaries will be reviewed and signed by PI before sharing them with research participants. Summaries will be shared through secure email, postal mail, or in person.

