### Section G: Sample Size/Data Analysis

#### G1. Sample Size

How many subjects (or specimens, or charts) will be used in this study?

Local: 200      Worldwide: 200

Please indicate why you chose the sample size proposed:

We will enroll a total of 200 participants, which achieves sufficient power for the primary and secondary aims. Although we expect slight attrition, the below-mentioned analyses allow for attrition without the loss of data. While MLM does not provide for specific power analyses, the suggested power rules range from 20 participants per group, per level. As such, to be conservative with our power estimates, we aim to enroll 200 participants to ensure we are sufficiently powered for our analyses, accounting conservatively for attrition (~7% at Step One; ~15% at Step Two).

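### Entry ratings double as the baseline in a single-arm design, so the fall in anxiety cannot by itself show the effectiveness of SC-CBT

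*Combined protocol and SAP*

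**What the plan says.** All references are to the combined protocol and SAP.

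- **Entry (F1, inclusion criterion 2).** A child needs a Clinical Severity Rating (CSR) of at least 4 on diagnoses endorsed on the "MINI-Kid) at baseline assessment, and the Pediatric Anxiety Rating Scale" above 12.
- **One visit for screening and baseline (F2, Initial Phone Screen).** Families who pass the telephone screen "will be invited for a screening visit (i.e., baseline assessment").
- **No second pre-treatment rating (F2, Informed Consent).** "After obtaining consent, participants will complete the baseline assessment and begin treatment". F1 lists "assessments that will occur at baseline, mid-treatment, post-treatment, and 3-month follow-up" and nothing between baseline and the start of treatment.
- **No untreated group (F2, Treatment).** "All participants will receive parent-led, stepped-care cognitive-behavioral therapy (SC-CBT").
- **Aim (Section D).** The first aim is to "examine the effectiveness of Stepped-Care CBT", and the expectation is causal: "We expect that through Stepped-Care CBT, children’s anxiety levels will lessen".
- **Analysis (G2).** Multilevel models of the repeated measures, plus a regression discontinuity analysis offered as a way to study treatment impact without randomisation. F2 shows which groups that analysis has: Step Two and maintenance, formed by response status at the mid-treatment assessment.

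G2 does not mention regression to the mean. Section C describes untreated anxiety in this population as getting worse over time.

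**The concern.** A child enters because ratings at one visit were high. Part of a high rating is transient, and that part tends to be gone at the next visit whether or not treatment works. Because the same visit supplies the starting point for change, some fall is built into the comparison. Normally a concurrent control or a second pre-treatment rating would absorb it. This design has neither.

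The regression discontinuity does not fill the gap. It compares two groups that have both had Step One, at a cut applied at mid-treatment. It offers no untreated comparison for baseline to mid-treatment, where regression to the mean mainly occurs, or for SC-CBT as a whole. Multilevel modelling handles repeated and missing measures but does not remove selection on the baseline.

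If a significant fall is read as the effectiveness named in Section D, the trial could credit SC-CBT with a change that an inert treatment would also show. If Step One response is judged against the same baseline, some children may also be classed as responders through regression alone. Responder status decides who steps up and is the outcome of the predictor model, and it would affect treatment costs.

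**Working it through.** **The plan's own figure.** G1 says "We will enroll a total of 200 participants, which achieves sufficient power for the primary and secondary aims", but gives no alpha, effect size, SD or reliability, so no power formula can be run. Its rule of 20 per group per level gives 20 × 2 × 3 = 120 for two groups and three levels. Allowing for both stated losses gives 120 / (0.93 × 0.85) = 152, not 200. The detectable change is therefore computed here.

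**Inputs.** From the documents: 200 children; losses of about 7% at Step One and 15% at Step Two; PARS cut above 12. Assumed: PARS is the outcome; scores of all children rated are normal; test-retest reliability *r* is 0.6 to 0.9; the cut excludes 10% to 70% of children rated; two-sided alpha is 0.05. The extra selection on CSR is ignored.

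**Detectable change.** Completers are 200 × 0.93 = 186 after Step One, or 200 × 0.93 × 0.85 = 158 if both losses apply to the whole cohort. In SDs of the change score, 80% power needs (1.960 + 0.842)/√n: 0.205 for 186 and 0.223 for 158. With 158, an observed mean change of 1.960/√158 = 0.156 is already significant.

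**Expected fall with no treatment effect and no natural change.** Let *a* be the cut in SD units of all rated children and λ = φ(a)/(1 − Φ(a)).

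- Fall, in SDs of all rated children: (1 − r)λ
- Variance of selected baselines: v = 1 + aλ − λ²
- SD of change: √[(1 − r)²v + 1 − r²]
- Fall in SDs of change: d = (1 − r)λ / SD of change
- Probability of a significant fall with 158 completers: Φ(d√158 − 1.960)

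Example with 50% excluded and r = 0.7: a = 0, λ = 0.798, fall = 0.3 × 0.798 = 0.239. Then v = 1 − 0.637 = 0.363, SD of change = √(0.09 × 0.363 + 0.51) = 0.737, and d = 0.239/0.737 = 0.325. The probability is Φ(0.325 × 12.57 − 1.960) = 0.98.

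| Share excluded by cut | λ | Fall, SD of all rated (r 0.9 to 0.6) | Fall, SD of change | Probability of a significant fall, n = 158 |
|---|---|---|---|---|
| 10% | 0.195 | 0.02 to 0.08 | 0.04 to 0.09 | 0.08 to 0.20 |
| 30% | 0.497 | 0.05 to 0.20 | 0.11 to 0.23 | 0.29 to 0.84 |
| 50% | 0.798 | 0.08 to 0.32 | 0.18 to 0.38 | 0.63 to >0.99 |
| 70% | 1.159 | 0.12 to 0.46 | 0.26 to 0.56 | 0.91 to >0.99 |

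Only the SD-of-change column may be set against 0.21 to 0.22.

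**In PARS points.** Assume a mean of 12 to 16 and an SD of 3 to 4 among children rated, with the cut at 12.5 for whole-number scores. The fall (1 − r) × SD × λ then runs from 0.07 to 1.41 points. Mid case (mean 14, SD 4, r = 0.7): a = −0.375, λ = 0.576, fall = 0.3 × 4 × 0.576 = 0.69 points from a selected baseline mean of 16.3. A simulation of this case gave 0.70.

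**The case against.** The strongest reply has five parts.

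1. **PARS is not named as the outcome.** F1 uses it for entry, and the list of measures is in an attachment that is not shown. This stands. With another anxiety scale the fall shrinks with that scale's correlation with the entry ratings, and the figures above become upper guides.
2. **Natural course may work against treatment.** A reader might infer that the bias always favours SC-CBT. The documents do not support that: Section C describes a worsening untreated course, which would hide benefit. Only regression to the mean has a known direction.
3. **Step One response is not defined against PARS.** F2 gives no numerical definition. A reader might infer that the response rate is inflated; the text supports only that it may be.
4. **The size rests on assumed inputs.** This also stands. The telephone screen may remove most low scorers, so the cut may exclude few children. At 10% excluded the artefact is small.
5. **Non-random assignment is acknowledged in G2, and any uncontrolled study has this limit.** True, but G2 presents the regression discontinuity as the answer, and it does not address this question.

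One point of reading: in the quoted criterion, the baseline timing attaches to the MINI-Kid. That PARS belongs to the same visit follows from the Initial Phone Screen and Informed Consent paragraphs, not from that sentence alone.

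**Conclusion.** The point holds as a limit on what Aim 1 can conclude. Selection and baseline share one visit, no child is untreated, there is no repeat pre-treatment rating, and the discontinuity analysis compares only Step Two with maintenance. A significant fall from baseline would not by itself show effectiveness.

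If PARS is the outcome, regression to the mean alone gives an expected fall of 0.04 to 0.56 SD of change across the assumed exclusion shares and reliabilities. It reaches the detectable 0.21 to 0.22 at 30% excluded only when reliability is near the low end, at 50% excluded over much of the range, and at 70% excluded throughout. The probability that an inert treatment shows a significant fall runs from 0.08 to above 0.99, so the artefact ranges from negligible to decisive. The natural-course component cannot be sized from the documents.

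A reader might go further and infer that any fall in this trial would be an artefact. The figures do not support that: the artefact is modest in points (0.07 to 1.41 under the assumptions above) and would not explain a large fall.

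**What to change.** 1. In Section D and G2, state the Aim 1 conclusion as change from baseline under SC-CBT, not as an effect of SC-CBT.
2. In G2, add a sensitivity analysis that reports the expected regression to the mean beside the observed change, over reliability 0.6 to 0.9. Use the PARS of all children rated at screening where it was recorded. The documents do not say that it is kept for children screened out, so otherwise report over a range of excluded shares, as in the table. State in advance that a significant fall within that range is not evidence of effectiveness.
3. F2 (Assessments) already plans participant-rated scales. If one measures anxiety and was not used for entry, report it as supportive. It reduces the bias through its lower correlation with the entry ratings but does not remove it, and it does nothing about natural course.

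The cost is some wording and a short calculation, with no new arm or visit. The downsides are a more modest claim and a correction that rests on an assumed reliability, hence the range.
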